## A. STUDY BACKGROUND AND PURPOSE

Under-immunization rates for childhood immunizations in the United States ranges from 8-20%. Previous studies have demonstrated that pediatric patients are most likely to be under-immunized for seasonal immunizations. The aim of this study is to explore the factors and facilitators contributing to measles immunization hesitancy. Secondly, we aim to explore the impact of hypothetical contexts on measles immunization hesitancy. The results of this study may identify potential disparities in measles immunization coverage and potential solutions for resolving those disparities.

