- Is your child immunized against COVID-19 for this season?
- Is your child immunized against RSV for this season?
  - Yes, the mother was immunized for RSV during pregnancy.
  - Yes, the child was immunized for RSV as an infant.
  - No
  - Unsure

All participants who identify that their child is under-immunized for measles (i.e. did not receive 1st MMR immunization at 1 year of age OR 2nd MMR immunization at 4 years of age) will go on to complete a comprehensive survey to assess immunization beliefs, to include:

- Please indicate that you agree or disagree with the below statements when thinking about getting your child up to date with all of their recommended immunizations?
  - Receiving all the recommended vaccines would significantly reduce my child's risk of getting sick (Vaccine Efficacy)
    - Agree or Disagree
  - Receiving all the recommended vaccines would be safe for my child (Vaccine Safety)
    - Agree or Disagree
  - Receiving all the recommended vaccines would be like performing an experiment on them (Vaccine Distrust)
    - Agree or Disagree
  - Receiving all the recommended vaccine will lead to long-term health problems for my child (Vaccine Long-Term Health Problems)
    - Agree or Disagree
  - Receiving all the recommended vaccines would be harmful to my child because of their current medical condition (Child's Medical Condition)
    - Agree or Disagree

- Agree or Disagree
- Receiving all the recommended vaccines is unnecessary because there is less risk now that young children will be infected with the virus or bacteria (Low Risk of Infection)
  - Agree or Disagree
- Receiving all the recommended vaccines is unnecessary because America has reached herd immunity for the virus or bacteria (low risk for infection)
  - Agree or Disagree
- The opinion of my child's doctor or healthcare provider will influence my decision about getting my young child vaccinated (Not recommended by Provider)
  - Agree or Disagree
- Getting children vaccinated against infectious diseases supports the community by stopping the spread of the disease among other children and adults (Stopping Community Spread)
  - Agree or Disagree
- I do not have enough information about all the recommended vaccines to be comfortable giving them to my child (lack of information)
  - Agree or Disagree
- I do not have a health care provider who has offered my child the vaccine (lack of healthcare access)
  - Agree or Disagree

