- I cannot miss work (have my child miss school) for a doctor's appointment to receive the vaccine (Social barriers)
  - Agree or Disagree
- I do not have transportation to get my child to the doctor's appointment to receive the vaccine (social barriers)
  - Agree or Disagree

– “Do you plan to get your child fully immunized for measles?”

- “Definitely not”
  - “Probably not”
  - “Unsure”
  - “Yes”

*Aim 2: Explore the impact of favorable immunization messaging on parental confidence in the measles in the under-immunized population.*

All guardians who complete the comprehensive survey will be randomized to receive one of four patient-centered immunization messages. The guardian will then be asked again if they plan to immunize their child against RSV this season and if they would accept the immunization if we administer it at the current visit.

- “Would you give your child the measles vaccination at this visit. This vaccine is known to prevent pneumonia that could lead to death and brain swelling that could lead to seizures or deafness?”
  - “Definitely not”
  - “Probably not”
  - “Unsure”
  - “Yes”
- “Would you give your child the measles immunization at this visit. This immunization is known to prevent pneumonia that could lead to death and brain swelling that could lead to seizures or deafness?”
  - “Definitely not”
  - “Probably not”
  - “Unsure”
  - “Yes”
- “Would you give your child the measles shot at this visit. This shot is known to prevent pneumonia that could lead to death and brain swelling that could lead to seizures or deafness?”
  - “Definitely not”
  - “Probably not”
  - “Unsure”
  - “Yes”
- “Would you give your child the measles medicine at this visit. This medicine is known to prevent pneumonia that could lead to death and brain swelling that could lead to seizures or deafness?”
  - “Definitely not”
  - “Probably not”
  - “Unsure”
  - “Yes”

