### **D. DATA ANALYSIS**

We will collect the following data: Age, Gender, Race, Ethnicity, State of residence, parental age, parental education level, household income, insurance status, parental report of immunization status and the reason for under-immunization if applicable. The sub-investigators will perform the data analysis at Albany Medical Center (AMC) with an AMC approved password protected PC. Storage of files will be on a password protected departmental drive. Use of a password protected master key document to store identifiers separately from other study variables, which will be collected and stored through REDCAPs.

Our primary outcome is the demographic variables and immunization beliefs that are associated with RSV under-immunization. Survey responses will be used to stratify outcomes according to child's age, Gender, Race, Ethnicity, State of residence, parental age, parental education level, household income, insurance status, and sources of health information. The secondary outcome is the improvement in immunization confidence (defined as converting from "definitely not intent, unsure about intent, or probably not intent" to "intent") stratified by patient-centered immunization messaging.

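### Aim 2 conversion compares a general measles plan with acceptance at the current visit, and the four arms differ only in one noun, so the trial can show the effect of the term but not of favorable messaging

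*Protocol*

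**What the plan says.** The comprehensive survey in Section B ends with the only measles intent item asked before the message: "Do you plan to get your child fully immunized for measles". It sets no time or place. Guardians are then randomized to one of four messages, and each message is itself a question. The first begins "Would you give your child the measles vaccination at this visit. This vaccine is known to prevent pneumonia" and goes on to name the complications prevented. The other three put immunization, shot or medicine in place of vaccination/vaccine.

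The text introducing the messages, in Section B and again in Section C (Aim 2), says: "The guardian will then be asked again if they plan to immunize their child against RSV this season". It adds that guardians will be asked whether they would accept it at the current visit. The listed items contain no repeat of the plan question, for RSV or for measles.

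Aim 2 is worded "Explore the impact of favorable immunization messaging on parental confidence", and Section A puts the matter as "we aim to explore the impact of hypothetical contexts on measles immunization hesitancy". Section D states: "The secondary outcome is the improvement in immunization confidence (defined as converting from" any of the three non-intent answers to intent, broken down by message. It does not say which post-message answer supplies intent.

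**The concern.** A before-after change measures a change in confidence only if the same question is asked twice. Here the first question concerns a general plan and the second an offer on the spot.

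The survey itself recognizes that access can be the obstacle, for example "I do not have a health care provider who has offered my child the vaccine" and "I do not have transportation to get my child to the doctor's appointment". A guardian held back only by access could move from Unsure to Yes when offered it in the emergency department and be counted as more confident, with no change in belief. Conversely, a guardian who was unsure and is persuaded, but prefers the child's own doctor, would answer other than Yes at the visit and be missed.

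The second problem is the comparator. Every arm carries the same benefit sentence and the same at-visit setting, so neither favorability nor context is varied by randomization. At stake is any statement that favorable messaging raised confidence, which is how Aim 2 is worded. If the RSV sentence is programmed into the survey as written, the repeated question will concern another disease and cannot follow up the baseline item.

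**Working it through.** The plan gives no figure to reproduce on this point. The check sets the items side by side and then works through what each comparison can identify.

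**1. Items before and after the message (Section B)**

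| Item | Listed before | Listed after |
|---|---|---|
| General measles plan | 1 | 0 |
| Measles acceptance at this visit | 0 | 4 (one per arm) |
| RSV plan this season | 0 | 0 (announced in the text, not listed) |

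No row has an item on both sides, so no matched pair exists for the Section D definition.

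**2. What differs between arms.** Each message has 33 words. Compared word by word, they differ only at words 8 and 13, both the noun, so 33 − 2 = 31 words are common to all four. With the noun masked, the four texts reduce to one. Arms without the benefit sentence: 0 of 4.

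**3. Access barriers in the survey.** Of the 13 listed belief statements, 3 concern access: no provider has offered the vaccine, missed work or school, and transport. An offer at the visit removes all three. This counts statements, not affected guardians.

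**4. What can be identified.** For arm j, write the conversion rate as

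c(j) = b + m + q + t(j),

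where b is conversion from re-asking alone, m the effect of the shared message content, q the effect of changing the question (including on-site access), and t(j) the effect of the term. The additive form and the values below are assumptions for illustration; none comes from the protocol. Take b = 0.20 and t(j) = 0:

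| m | q = −0.15 | q = 0 | q = +0.15 |
|---|---|---|---|
| 0 | 0.05 | 0.20 | 0.35 |
| 0.10 | 0.15 | 0.30 | 0.45 |
| 0.20 | 0.25 | 0.40 | 0.55 |

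A message with no effect (m = 0, q = +0.15) gives 0.35. A message with a real effect (m = 0.20, q = −0.15) gives 0.25. The order is reversed, so observed conversion does not reveal m.

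Between arms j and k, c(j) − c(k) = t(j) − t(k). The terms b, m and q cancel. The randomized contrast is sound, but it concerns only the noun.

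**The case against.** The strongest reply is that Section D breaks conversion down by message, which reads naturally as a comparison across arms. The baseline item precedes randomization and the change of question is common to all arms, so that comparison is not biased. The protocol nowhere says it will attribute overall conversion to messaging, and favorable could simply mean whichever term is best received. All of this stands for the between-arm comparison of terms. It does not rescue the outcome as a measure of improved confidence, and neither the aims nor Section D says that the term is the object of study. If it is, the wording should say so.

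A second reply is that RSV is carry-over text (Section D makes the same slip in the primary outcome) and that the introductory text already plans two post-message questions. That is probably right about intent, but correcting the disease name still leaves no repeated plan item listed. Section C refers to a data collection form that is not shown. The form might hold such an item, though that reference sits beside the chart data.

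A third reply is that a statistical analysis plan can name the item that defines intent. It can choose among answers collected, but it cannot supply a question never asked or an arm never randomized.

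Finally, a stray response line after the medical-condition statement means that a belief statement may have been lost in the text, so 13 counts what is legible. The argument does not depend on it.

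**Conclusion.** The concern holds and should be fixed. As listed, conversion pairs two different measles questions; following the introductory text literally, it would pair two different diseases. Overall or within-arm conversion cannot be attributed to favorable messaging, because all 4 post-message items change the question and no arm lacks the benefit sentence. Between-arm contrasts of the term (vaccine, immunization, shot, medicine) remain valid.

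The size of the shift cannot be derived from the protocol and none is claimed. The conclusion rests on the survey items as the protocol lists them.

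**What to change.** 1. In Sections B and C, correct RSV to measles in the sentence announcing the repeated question. List the baseline measles plan item, in identical words, after the message.
2. In Section D, define conversion on that matched pair. Analyze acceptance at the visit as a separate outcome, compared between arms.
3. Ask the at-visit item, which carries the message, before the repeated plan item.
4. In Sections A and B (Aim 2) and in the secondary outcome, state the question as the effect of the term used, and draw conclusions only from between-arm contrasts.

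The cost is one extra survey item and wording changes in four sections. There are three downsides. The repeated item uses the word immunized in every arm and could dilute the noun contrast, which is why the at-visit item comes first. The at-visit answer may then influence the repeated plan answer. And Aim 2 makes a narrower claim.

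Precision will also limit those contrasts. If the 8–20% under-immunization range in Section A applied to measles here (an assumption), 800 guardians would give 800 × 0.08 = 64 to 800 × 0.20 = 160 randomized, or 16 to 40 per arm. Keeping the broader aim would instead need an arm with no message or a neutral one, which would split the same guardians five ways.

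### In Aim 2 the randomised noun sits inside the only written post-message measles question, and a 'Yes' in the *medicine* arm need not mean intent to immunize

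*Protocol*

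**What the plan says.** Section B (Aim 1, comprehensive survey) puts one baseline intent question to every guardian of a measles under-immunized child: "Do you plan to get your child fully immunized for measles". The four options run from 'Definitely not' to 'Yes'.

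Under Aim 2 these guardians are "randomized to receive one of four patient-centered immunization messages". Four items follow, each with the same four options:

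- "Would you give your child the measles vaccination at this visit. This vaccine is known to prevent pneumonia"
- "Would you give your child the measles immunization at this visit. This immunization is known to prevent pneumonia"
- "Would you give your child the measles shot at this visit. This shot is known to prevent pneumonia"
- "Would you give your child the measles medicine at this visit. This medicine is known to prevent pneumonia"

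The rest of the wording is the same in all four.

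The paragraph that introduces these items also says: "The guardian will then be asked again if they plan to immunize their child against RSV this season". It adds that guardians will be asked whether they would accept the immunization at the current visit. Section C (Aim 2) repeats this.

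Section D states: "The secondary outcome is the improvement in immunization confidence". It defines improvement as a move from any of the three non-intent answers to intent, and stratifies it by message. It does not name the post-message item to be used.

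**The concern.** Each Aim 2 item is both the message and the question answered. If its answer is what section D counts, the thing being varied is also part of the instrument that measures its effect.

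For *vaccination*, *immunization* and *shot* this matters little, because all three plausibly name the same act. *Medicine* is different. Neither sentence of that item links the product to vaccination, and the question is asked in an emergency department, where children are given medicines. A guardian who has just answered 'Probably not' on measles immunization could accept a *measles medicine* without any change of view on immunization, and would then be counted as converted.

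This is the study's only randomised comparison. A result favouring *medicine* could be taken up as a way of raising confidence when it partly reflects guardians not recognising a vaccine. No later analysis can separate the two explanations if no common item was collected.

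**Working it through.** **1. The written items side by side.**

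| Item | Noun | Asks about | Same in all arms? |
|---|---|---|---|
| Baseline (section B) | immunized | plan to be fully immunized for measles | yes |
| Arm 1 | vaccination / vaccine | acceptance at this visit | no |
| Arm 2 | immunization | acceptance at this visit | no |
| Arm 3 | shot | acceptance at this visit | no |
| Arm 4 | medicine | acceptance at this visit | no |
| Announced repeat (sections B and C) | immunize, RSV | plan for this season | described in prose only |

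Two things follow. The only post-message measles items written with response options are the four arm-worded ones. And none of them, not even the *vaccine* item, repeats the baseline question: baseline asks about a plan, the arm items about acceptance today. Conversion from one to the other mixes two questions in every arm.

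**2. Which answer is scored.** The announced follow-up has two parts, plan and acceptance at this visit. The arm-worded items fit the second part. No measles item is listed for the first, and the sentence names RSV. Section D speaks of intent without pointing to an item. Scoring the arm-worded answer is thus the reading that the written items support, but it is not stated.

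**3. Size.** The document gives no figure to reproduce and no rate of misreading. An illustration needs two assumed inputs:

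- p = true conversion to immunization intent, taken as equal in all arms;
- m = share of the remaining guardians in the *medicine* arm who say 'Yes' without understanding that the vaccine is meant.

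Apparent conversion = p + (1 − p) × m, so the spurious gain = (1 − p) × m.

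With p = 20%:
- m = 10%: 0.20 + 0.80 × 0.10 = 0.28, a gain of 8 points;
- m = 30%: 0.20 + 0.80 × 0.30 = 0.44, a gain of 24 points.

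| True conversion p | m = 10% | m = 20% | m = 30% |
|---|---|---|---|
| 10% | 9 points | 18 points | 27 points |
| 20% | 8 points | 16 points | 24 points |

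These values restate the assumption on m, reduced by the factor (1 − p). They are not evidence that misreading occurs at that rate.

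I do not carry this through to a chance of a significant result. The number randomised is not stated. It would have to be built from about 800 enrolled and a general childhood under-immunization range of 8-20%, which is not a measles rate, and then reduced to guardians not already at 'Yes'.

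**The case against.** **Wording is the intervention.** Aim 2 studies messaging, and the items are otherwise identical. If the question is which term guardians accept, acceptance under that term is a legitimate outcome. This stands: varying the noun is not an error. The difficulty arises only when acceptance of the term is labelled immunization confidence, and mainly in one arm of four.

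**A common question is already announced.** A reader might infer that the arms share no common outcome measure at all. The documents do not support that as a flat statement. Sections B and C say that guardians will be asked again about their plan, which points back to the arm-neutral baseline question and suits section D's use of intent. The RSV reference may be carried over from another study, since section D's primary outcome also names RSV. Section C refers to a data collection form, not shown here, which might list the item. What remains is that, as written, the announced item names a different disease, has no text, and is not tied to the outcome.

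**Context makes the meaning clear.** Before randomisation, guardians answer thirteen belief statements, all referring to vaccines or vaccination, and then the measles immunization question. The message also describes prevention. This should reduce misreading, perhaps greatly. It does not exclude it, and no written item would detect it.

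**The outcome is secondary and exploratory.** That is true and limits the weight of the point, although this outcome is the whole of the randomised part.

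**Conclusion.** The point holds in limited form. The randomised noun is part of the only post-message measles question that is written out. In the *medicine* arm that question does not identify the product as a vaccine, so a 'Yes' there is not securely immunization intent.

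This matters for the secondary outcome if the arm-worded answer defines conversion. The written items point to that, but section D does not say it, so it would be too strong to assert that the protocol definitely scores a *medicine* 'Yes' as conversion. It would also be too strong to extend the problem of meaning equally to all four arms, or to attach a size to it as a finding. The 8-24 points (p = 20%, m = 10-30%) rest wholly on assumed inputs, and the true share could be close to zero.

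The change is worth making because it is cheap and a common measure cannot be recovered after data collection.

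**What to change.** - Keep the four arm-worded items as they are.
- After them, ask every arm the baseline measles question again, word for word and with the same four options. If acceptance at this visit is also wanted, add one item, identical in every arm, that names the measles vaccine.
- Change RSV to measles in the Aim 2 follow-up sentence (sections B and C) and in the primary outcome (section D). The brief-survey question on RSV immunization is a separate item and is not affected.
- In section D, name the repeated common item as the one that defines conversion.
- Report the arm-worded answer separately as acceptance of the term, by arm, with the number who say 'Yes' to it but not to the common item. That count shows directly how far the two answers diverge.

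The cost is one or two extra tablet items and a few edited sentences. There is a small statistical downside. Answers to the common item may be pulled toward consistency with the arm-worded answer just given, and a plainly named vaccine may dilute a pure wording effect. The retained arm-worded answers still show that effect.

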**C. SUBJECT POPULATION (WHO, WHAT, WHERE)**

Aim 1: Guardians of patients 1 year to 6 years old presenting to the pediatric emergency department 6/1/2025 and 6/1/2026 will be eligible. I expect that we will enroll ~800 parental encounters here at AMC. Parents of children meeting the above inclusion and exclusion criteria will be approached for consent to participate in the study by convenience sampling weekdays 0900-1700. All consenting guardians will complete a brief survey to assess parental demographics and child immunization history. All participants who identify that their child is under-immunized for measles (i.e. did not receive 1st MMR immunization at 1 year of age OR 2nd MMR immunization at 4 years of age) will go on to complete a comprehensive survey to assess immunization beliefs.

Aim 2: In a private location, research assistants (RA) will randomly sample patients between 1 and 6 years of age in the pediatric ED and approach the patient's caregivers for participation in the survey if

eligible. Caregivers will give written consent to participate in the survey. Caregivers will complete this survey in the ED on a private tablet. All guardians who complete the comprehensive survey will be randomized to receive one of four patient-centered immunization messages. The guardian will then be asked again if they plan to immunize their child against RSV this season and if they would accept the immunization if we administer it at the current visit.

